## **8.2 Study Drug Allocation and Prescribing Procedures**

In Part A, in order to confirm eligibility for study participation based on the screening tests, the investigator or a person designated by the investigator will contact the registration center by fax. The investigator will prescribe study drug to the subject after confirming that the subject is eligible for the study based on a fax received from the registration center.

In Part B, the investigator or a person designated by the investigator will contact the registration center by fax to confirm the subject's eligibility at the start of the treatment period. After confirming, on the basis of a fax received from the registration center, that the subject is eligible, the investigator will prescribe the subject the study drug for the group to which the subject has been assigned. The investigator or a person designated by the investigator will enter the group to which the subject has been assigned in the eCRF.

Subjects will be assigned a 4-digit number, with the first signifying the Part and Cohort, the second signifying the investigational site, and the last two digits constituting a series number within the cohort at the investigational site. This 4-digit number will be used by the investigational sites to identify the specimens that will be used to assess the PK and pharmacodynamics. These numbers will be noted on the specimen tubes that are provided for measurement, and will be used instead of the subject identification numbers for reporting the measurement results. These numbers will not be replaced by the last 3 digits of the subject identification numbers.

## **8.3 Randomization Code Creation and Storage**

The randomization manager (or a person designated by the study sponsor) will prepare a randomization table. The randomization information will be stored in a safe location, and will only be accessible to authorized personnel.

## **8.4 Control and Disposal of Drugs Provided by the Study Sponsor**

The study drug controller will receive the written procedures prepared by the study sponsor specifying the handling, storage, and control of study drug, and will appropriately control the drugs provided by the study sponsor in accordance with these written procedures. The investigators will also receive these procedures from the study sponsor. These procedures will describe the procedures that will have to be followed to ensure that the receipt, handling, storage, control, and prescribing of the study drugs provided by the study sponsor, as well as the recovery of unused drugs from subjects and their return to the study sponsor, or their disposal, are carried out appropriately and reliably.

The study drug controlled will promptly return to the study sponsor any unused drugs once the study has been completed at the investigational site in question.

## 9.0 STUDY PLAN

### 9.1 Study Procedures

The following sections describe the study procedures and data to be collected. In principle, the same investigator will perform examinations and testing, observations, and evaluations of subjects. The Schedule of Study Procedures is shown in [Appendix A](#) to [Appendix E](#).

#### 9.1.1 Informed Consent

The requirements of the informed consent are described in Section 15.2.

Informed consent must be obtained from the subject before any protocol-directed procedures are performed.

A unique subject identification number will be assigned to each subject at the time that informed consent is explained. The same subject number will be used throughout the study.

#### Informed Consent for Pharmacogenomics

Informed consent for the storage and banking of the blood sample for pharmacogenomics (PGx) testing in this study must be obtained separately before collection. The provision of consent to collect and analyze the PGx sample is independent of consent to the other aspects of the study.

#### 9.1.2 Demographics, Medical History, and Treatment History

Demographic data will include date of birth, sex, and smoking history at screening. The items listed below will be checked with regard to prostate cancer [16]. The findings will be input to the eCRF.

- Date of diagnosis and diagnostic method used
- Gleason classification (pattern 1 to 5 and score) at most recent assessment and date of assessment
- Tissue type and extent of differentiation
- Treatment history (including medication history)
- TNM classification (at time of diagnosis)
- Prostatectomy yes/no, total resection yes/no, date of surgery
- High intensity focused ultrasound yes/no, completion date
- Radiation therapy yes/no, completion date
- History of other therapy yes/no, mode of therapy, start date, completion date

The medical history will include clinically relevant diseases or conditions associated with the targeted disease that disappeared or ended within the past 1 year from the date of

informed consent. If a symptom or disease is still present, it will be considered a comorbidity (concurrent medical condition) (see Section 9.1.18).

Previous therapeutic drugs used (medication history) will include all drugs that were discontinued within 28 days before the date of informed consent and are relevant to the eligibility criteria.

### 9.1.3 Physical Examination

A physical examination will be conducted for the parts of the body listed below (interview, visual inspection, auscultation, palpation, percussion, etc.).

(1) eyes, (2) ears, nose, and throat, (3) cardiovascular system, (4) respiratory organs, (5) digestive organs, (6) skin, (7) extremities, (8) musculoskeletal system, (9) nervous system, (10) lymph nodes, (11) urogenital organs, (12) other

The investigator will evaluate abnormal findings discovered in the pre-administration physical examination for clinical relevance and record the results in the source data. Findings and changes considered to be clinically relevant will be input as PTEs or comorbidities at the proper locations in the source data and eCRF as described in Sections 10.0 and 9.1.18.

### 9.1.4 Weight, Height, and ECOG Performance Status

Weight and height will be measured. Weight will be measured in kilograms to the first decimal place, and height will be measured in centimeters to the closest integer. In addition, the ECOG performance status will be measured in accordance with Appendix G.

### 9.1.5 Vital Signs

Measurement of vital signs will include temperature (axillary), seated blood pressure (systolic and diastolic after resting at least 5 min) and heart rate (bpm). Measurements will be taken after the subject has been sitting for 5 min.

### 9.1.6 Electrocardiogram

A 12-lead ECG will be performed. Measurements will be taken after the subject has been in supine position for 5 min. The investigator (or a specialist at the medical institution) will assess the results by the following categories: Normal range ("Within Normal Limits"), Abnormal but not clinically significant ("Abnormal, Not Clinically Significant"), or Abnormal and clinically significant ("Clinically Significant").

The following parameters will be transferred from the subject's ECG recording to the eCRF: heart rate, QT interval, PR interval, QRS duration, and RR interval.

In determining the QTc value, Bazett corrected QT (QTcB) and QTcF will be calculated using the Bazett formula ( $QT/RR^{0.5}$ ) and Fridericia formula ( $QT/RR^{0.33}$ ), respectively.

### 9.1.7 Imaging Assessment

CT or MRI (thoracic, abdominal, and pelvic regions) and bone scintigraphy will be performed during screening to verify that there are no distant metastatic lesions. If measurements were taken within 28 days before the start of study drug administration, the results of diagnostic imaging and tests conducted before obtaining informed consent can be used. CT or MRI and bone scintigraphy will also be performed on the days stipulated in the clinical trial schedule ([Appendix A](#) to [Appendix C](#)) to check for new lesions. Disease progression will be determined by the presence or absence of new lesions based on the items evaluated in diagnostic imaging. Diagnostic imaging will also be performed as needed in Part A if abnormal findings appear in other tests and examinations during administration of the study drug.

### 9.1.8 Clinical Laboratory Tests

Specimens will be handled according to the procedures described in a separate document. A general guideline for the total amount of blood to be collected in this study is shown in Section 9.5.

Samples for clinical laboratory tests will be collected after at least 10 hours of fasting on the days stipulated in the Schedule of Study Procedures ([Appendix A](#) to [Appendix E](#)). Samples to be collected for each laboratory test are shown in [Table 9.a](#).

**Table 9.a Clinical Laboratory Tests**

Hematology	Chemistry	Metabolic Panel	Urinalysis
RBC	Total protein	Triglycerides	pH
WBC	Albumin	Total cholesterol	Specific gravity
Hemoglobin	Glucose	HDL cholesterol	Protein (qualitative)
Hematocrit	Creatinine	LDL cholesterol	Glucose (qualitative)
Platelet count	BUN	TSH	Occult blood (qualitative)
Differential WBC (neutrophils [including absolute count], basophils, eosinophils, lymphocytes, monocytes)	Uric acid	HbA1c	Ketones (qualitative)
	Total bilirubin		Urobilinogen (qualitative)
	ALT		Bilirubin (qualitative)
	AST		
	LDH		
	γ-GTP		
	ALP		
	CK(CPK)		
	Na		
	K		
	Cl		
	Ca		
	P		
	PT-INR		

Tests to be conducted when determining eligibility

(to be performed only when deemed necessary)

HIV test; hepatitis tests including HBsAg and anti-HCV; serologic test for syphilis

---

The above clinical laboratory tests will be performed at the medical institution. The investigator will evaluate and archive reported clinical laboratory test findings.

When the ALT or AST levels are  $> 3 \times \text{ULN}$ , retesting (at least ALP, ALT, AST, total bilirubin,  $\gamma$ -GTP, and PT-INR) will be performed within 48 to 72 hours (within 7 days at the latest).

(See Section 7.5 for the criteria for the withdrawal from the study. See Section 10.2.3 for the reporting of LFT abnormalities in cases where the ALT or AST level exceeds  $3 \times \text{ULN}$ , and the total bilirubin level exceeds  $2 \times \text{ULN}$  or the PT-INR exceeds 1.5.)

The investigator will archive the reference ranges for the clinical laboratory tests, including the history.

All clinically relevant, abnormal laboratory test values will be input in the source data and eCRF of the subject as AEs, etc. All clinically relevant, abnormal laboratory test values verified by retesting will be followed up in all subjects until the abnormal value returns to an acceptable level or there is a sufficient explanation for the observed change.

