## 7.0 SELECTION AND DISCONTINUATION/WITHDRAWAL OF SUBJECTS

All inclusion and exclusion criteria, including test results, need to be checked before study treatment initiation (Part A) or randomization (Part B).

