  - b. Patients with uncontrolled hypertension (systolic blood pressure > 150 mmHg and diastolic blood pressure > 90 mmHg at 2 separate measurements taken no more than 60 minutes apart at screening). Patients whose blood pressure is brought under control by antihypertensive medication may be rescreened.
  - c. Patients with myocardial infarction, unstable symptomatic ischemic heart disease, arrhythmias of CTCAE Grade > 2, thromboembolism (deep vein thrombosis, pulmonary embolism, or symptomatic cerebrovascular events), or other heart diseases (eg, pericardial effusion, restrictive cardiomyopathy). However, chronic stable atrial fibrillation controlled by stable anticoagulant therapy will be allowed.
13. Patients with bilateral hydronephrosis or bladder neck outlet obstruction.
  14. Known hypersensitivity to TAK-385, TAK-385 excipients, or GnRH antagonists.
  15. Patients with a past history of gastrointestinal tract treatments (including gastrectomy) or gastrointestinal disease that could affect the drug absorption or tolerability (malabsorption, esophageal reflux, peptic ulcer, erosive esophagitis).
  16. Patients positive for hepatitis B surface antigens (HBsAg), hepatitis C virus (HCV) antibodies, human immunodeficiency virus (HIV) antibodies, or serologic test for syphilis, or with life-threatening disease other than cancer, at screening.
  17. Clinically relevant ECG abnormalities, or the following ECG abnormalities, at screening.
    - a. Q-wave infarction, unless identified 6 or more months prior to TAK-385 treatment initiation
    - b. QTcF interval > 450 msec (when calculating the QTc interval, Fridericia's equation  $[QT/RR^{0.33}]$  will be used)
  18. Patients with congenital QT prolongation.
  19. Current use of Class 1A or Class 3 antiarrhythmic medications.
  20. New York Heart Association [18] Class III or IV heart failure ([Appendix H](#)).
  21. Patients with clinical laboratory abnormalities suggesting clinically relevant underlying disease, or with any of the following abnormal results, at screening.
    - Serum creatinine  $\geq 2.0$  mg/dL
    - ALT or AST  $\geq 1.5 \times$  ULN for the investigational site
    - Total bilirubin  $\geq 2 \times$  ULN for the investigational site
    - Neutrophil count < 1,500/mm^3, platelet count < 100,000/ $\mu$ L, hemoglobin < 10.0 g/dL

- Results of heart-related tests (creatine kinase MB [CK-MB] and cardiac troponin T) exceeding the investigational sites reference value.

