#### 9.3.1 Screening

Observations and tests will be performed within 28 days prior to the first dose of study drug to confirm subject eligibility for study participation based on the inclusion and exclusion criteria presented in Section 7.0. See Section 9.1.23 for the preparation of records for subjects withdrawing from the study during screening.

The following tests, observations, and assessments will be performed at screening.

- Informed consent
- Demographics, medical history, concurrent medical condition, treatment history
- Physical examination
- Vital signs
- Weight, height, and BMI
- ECOG performance status
- HBsAg, HCV, and HIV antibody and serologic test for syphilis  
If the institutional review board judges it necessary, these tests will be performed only for subjects determined by the investigator to be at high risk for hepatitis B or C or HIV infection.
- 12-lead ECG
- Chest X-ray examination
- Imaging assessments
- Clinical laboratory tests (hematology, chemistry, metabolic panel, and urinalysis)
- Cardiac tests
- Pharmacodynamic assessments (serum testosterone, LH, FSH, DHT, and SHBG)
- Tumor marker (PSA)
- Concomitant medications
- Concomitant therapies
- PTEs

The following tests will be performed only in Part B.

- Ophthalmological examinations
- Bone mineral density
- QOL assessments

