**Table 9.b Blood Sample Volumes and Numbers of Samples Collected (Part A)**

Type of Sample	Volume of Blood Collected Per Sample (mL)	Number of Samples (Times) Collected	Total Volume (mL)
Hematology tests	12	7	84
Chemistry tests	9.2	7	64.4
Metabolic panel tests	5.6	4	22.4
Cardiac tests	4.4	1	4.4
Tumor marker	2.0	2	4
HIV, etc. tests*1	5.6	1	5.6
Pharmacodynamic assessments	7.0	9	63
PGx sample collection	5	1	5
PK assessments	3	37	111
Total Volume of Blood Collected			363.8

\*1: Will be performed only when judged necessary

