#### 10.1.5.1 Liver Function Test Abnormalities

LFT abnormalities were identified as specific AEs because nonclinical studies in monkeys revealed LFT abnormalities and because clinical studies on oral GnRH antagonists with the same backbone structure as TAK-385 have revealed elevated AST and ALT as common treatment-related AEs.

The management of LFT abnormality AEs is presented in Table 8.c of the protocol. When ALT or AST levels are  $> 3 \times$  ULN, retesting will be performed within 48 to 72 hours (within 7 days at the latest). As soon as they become aware that ALT or AST levels are  $> 3 \times$  ULN, investigators will discuss detailed information on affected subjects and other potential causes with the sponsor to review whether the administration of study drug should be discontinued immediately.

If ALT or AST levels are  $> 3 \times$  ULN and total bilirubin levels are  $> 2 \times$  ULN or the PT-INR is  $> 1.5$ , and investigators conclude that the levels cannot be explained by any factor other than study drug based on the results of retesting, then they will be handled as serious AEs.

When LFT abnormalities correspond to the criteria in Section 7.5, investigators will immediately discontinue administration of study drug and will perform appropriate follow-up.

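### Exclusion 16 depends on hepatitis, HIV and syphilis serology that other parts of the protocol leave optional or unscheduled, so an untested hepatitis carrier can enter a trial that watches the liver closely

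*Protocol*

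**What the plan says.** All references are to the current protocol text (Amendment 2).

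- Section 7.2, exclusion 16, opens "Patients positive for hepatitis B surface antigens (HBsAg), hepatitis C virus (HCV) antibodies" and goes on to HIV antibody and syphilis serology, all judged at screening.
- Section 7.0 gives the general rule: "All inclusion and exclusion criteria, including test results, need to be checked before study treatment initiation (Part A) or randomization (Part B".
- Table 9.a (Section 9.1.8) groups "HIV test; hepatitis tests including HBsAg and anti-HCV; serologic test for syphilis" as eligibility tests and labels them "to be performed only when deemed necessary".
- Tables 9.b (Part A) and 9.c (Part B) budget 5.6 mL for this sample. The footnote to each reads "Will be performed only when judged necessary".
- Section 9.3.1 lists the four tests among those done at screening. It then lets the IRB narrow this: "these tests will be performed only for subjects determined by the investigator to be at high risk for hepatitis B or C". The same sentence names HIV as a third risk.
- Appendices A and B, the visit schedules, contain no serology row.

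On the liver, Section 10.1.5.1 states that "LFT abnormalities were identified as specific AEs", and no other special-interest category is named. Section 6.1.2.1 gives ALT, AST, bilirubin and PT-INR their own confirmation rule within the dose-limiting toxicity (DLT) definition.

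**The concern.** An exclusion defined by a test result works only if the test is done. No section says how exclusion 16 is judged in a subject without a result. Serology stands out here. The ECG, chemistry, haematology and HbA1c exclusions all rest on tests scheduled at screening, and Section 9.1.9 has CK-MB and troponin T measured then too.

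Two things are at stake. A carrier could be treated against the protocol's own exclusion, with a drug whose liver effects the protocol singles out for monitoring. And if his enzymes rise, there is no baseline serology to help separate a background cause from a drug effect. Part A cohorts start with 3 subjects, so a single event counted as a DLT changes what happens next.

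**Working it through.** **1. The plan's own figure.** The only design probability stated is in Section 13.3: about 80% chance of seeing an adverse event of true incidence 10% with 15 subjects per group. 1 − 0.9^15 = 0.794, so it reproduces per group (for 30 subjects, 1 − 0.9^30 = 0.958). This point does not alter it.

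**2. The passages side by side.**

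| Place | Status of the serology |
|---|---|
| Section 7.0 with exclusion 16 | Result needed before entry |
| Section 9.3.1 | Done at screening, or high-risk subjects only if the IRB so decides |
| Table 9.a; footnotes to Tables 9.b and 9.c | Only if thought necessary |
| Appendices A and B | Not scheduled |

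A site following Table 9.a can leave a subject untested and still consider his eligibility complete. Under the Section 9.3.1 restriction, a subject not judged high risk is also untested.

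**3. What else could stop a carrier.** Exclusion 21 bars ALT or AST at or above 1.5 × ULN, total bilirubin at or above 2 × ULN, and laboratory findings that point to relevant underlying disease. Exclusion 12 covers uncontrolled, clinically significant liver disorders. Exclusions 22 and 23 cover examination findings and investigator judgement. A carrier without symptoms or abnormal findings, and with liver tests below those limits, can pass all four.

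**4. Chance that a carrier enters (illustration).** The documents give no prevalence. Assume a share p of otherwise eligible subjects are undetected carriers and that nobody is tested. P(at least one) = 1 − (1 − p)^n.

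| p | n = 3 | n = 30 (Part B) | n = 54 (24 + 30, the maximum) |
|---|---|---|---|
| 0.5% | 1.5% | 14% | 24% |
| 1% | 3.0% | 26% | 42% |
| 2% | 5.9% | 45% | 66% |
| 3% | 8.7% | 60% | 81% |

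**5. Effect of one background DLT in a cohort (conditional illustration).** Table 6.c passes a cohort at 0/3 or 1/6. With true drug DLT rate d, P(pass) = (1 − d)^3 + 3d(1 − d)^2 × (1 − d)^3. If one of the first 3 subjects already has a hepatitis-related event counted as a DLT, the other 5 must all be free of DLTs: (1 − d)^5. At an assumed d = 10%:

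- without the background event: 0.729 + 0.177 = 0.906;
- with it: 0.9^5 = 0.590.

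At d = 5% the pair is 0.973 and 0.774; at d = 20% it is 0.709 and 0.328. These figures apply the table alone, before any judgement by the study monitoring committee (SMC).

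**6. Sample volume.** The Table 9.b rows sum to 84 + 64.4 + 22.4 + 4.4 + 4 + 5.6 + 63 + 5 + 111 = 363.8 mL, the stated total. The 5.6 mL is therefore already counted. The Table 9.c total of 524.8 mL includes it too.

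**The case against.** The best defence is that Section 9.3.1 is the operative procedure and the label in Table 9.a is shorthand for its high-risk restriction. The blood-volume tables are described as guidelines. Amendment 1 edited this very entry of Table 9.a, adding syphilis and keeping the label, which suggests a deliberate choice. A registration centre also confirms eligibility before drug is prescribed. This shows the optional testing may be intended. It does not reconcile it with Section 7.0 and exclusion 16, because neither exempts low-risk subjects.

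The objection is stronger on consequences. Several things that a reader might infer are not supported:

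- **That DLTs are essentially liver enzyme rises.** Liver tests are one limb. Any treatment-related toxicity of Grade 3 or higher and certain QT findings also count.
- **That hepatitis would go unnoticed after a rise.** Section 10.2.3 asks about other acute liver disease as well as hepatitis A and B, Appendix I lists viral serology, and Section 10.1.5.1 requires other causes to be discussed with the sponsor.
- **That a background rise would automatically be a DLT.** It must be judged treatment-related, and unclear cases go to the SMC. Still, Section 10.1.7 classes an event as related if drug involvement is arguable even when another cause may be responsible, so it could be counted.
- **That a second such event necessarily halts the cohort.** Section 6.1.1 lets the dose be judged tolerable after SMC consultation despite 2 or more DLTs. Two carriers among 6 subjects is also unlikely: 1 − 0.97^6 − 6(0.03)(0.97^5) = 1.2% at 3% prevalence, and 0.15% at 1%.

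**Conclusion.** The inconsistency is real and stands in the current text: the protocol gives the same four tests incompatible statuses, and a hepatitis carrier with near-normal liver tests can be enrolled untested despite exclusion 16. It is worth correcting, because it bears on the safety of that subject and on attribution of the one special-interest event the protocol names.

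Its size cannot be fixed from the documents. The 26% to 60% for Part B assumes a carrier prevalence of 1% to 3% and no testing at all. A reader might take it as the chance that the trial misreads liver toxicity. It is not: Part B has no DLT rule, and nothing in the documents links carriage to an enzyme rise, a misattribution or a wrong cohort decision. The fall from 91% to 59% likewise holds only if a background event has already been counted as a DLT and the true drug rate is 10%. The conclusion rests on comparing the passages, not on these figures.

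**What to change.** Reconcile Section 7.0, exclusion 16, Table 9.a, Section 9.3.1, the footnotes to Tables 9.b and 9.c, and Appendices A and B so that each test exclusion 16 relies on has one stated status.

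- **Hepatitis B surface antigen and hepatitis C antibody:** require a result from every subject before treatment (Part A) or randomisation (Part B). Accept a recent site result within a stated window. Remove the optional label for these two tests and add a screening row to Appendices A and B.
- **HIV and syphilis:** either require a result as well, or reword exclusion 16 to match the restricted testing. The risk condition in Section 9.3.1 names hepatitis B, hepatitis C and HIV but not syphilis, so syphilis needs its own wording if testing stays restricted.

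The cost is two routine assays per subject on the 5.6 mL sample already in the blood totals, wording changes in the places listed, and possibly a few more screen failures. No treatment rule or analysis changes.
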